#### **Data collection tools:**

To protect the privacy of patients, the data collected in the study is stored completely de-identified. A code will be linked to the information provided, and answers are entered into a computer database using this code. No personal identifiers will be linked to the participant's information in the database. All of this information in the computer is password protected. The code will be linked to the participant's University of Colorado Hospital medical record number in a separate computer database. The PI will keep the surveys completed on paper in a locked cabinet.

#### **E.** Potential Scientific Problems:

To maximize scientific integrity this study was peer reviewed by the Colorado Department of Health and Safety (CDPHE) before receiving funding. We do not expect problems with recruitment because of the high level of interest and publicity regarding cannabis research, especially the CDPHE funded studies. In addition, we have a large population of PD patients, since we see over 2000 PD patients in our Movement Disorders clinics annually, including UCH, VAMC, and Denver Health, and will have 14 movement disorders providers assisting recruitment.

#### F. Data Analysis Plan:

Intention to treat concept is followed. In order to minimize data entry errors a double data entry system will be used.

If study participant agrees, the de-identified data would be shared within CDPHE Marijuana grantee consortium for future research.

The analysis will be performed in accordance with the analysis plan devised prior to unblinding. Baseline variables will be examined for equality between the two sequence groups. The primary, secondary and exploratory outcomes will be analyzed as below from baseline to the end of 2.5 mg/kg/day.

Primary Specific Aim: To evaluate the efficacy of CBD on motor symptoms in PD. The data will be analyzed to compare two randomized independent samples, CBD and placebo. Means and confidence intervals will be presented for the pre and post outcome values by treatment, and for the change scores between pre and post treatment within treatment group. A two independent sample T-test will compare the means of the change scores between the treatment groups. We will test the null hypothesis of no treatment effect. Longitudinal regression models will be fit for further analysis, including adjusting for covariates if necessary.

Secondary Specific Aim is to examine safety and tolerability of CBD and the effect of CBD on severity and duration of intractable tremor and other symptoms in PD.

Safety and tolerability and will be assessed in five ways:

- Frequency of study-related adverse events at each dose level collected at study visits. Analysis (frequency of study-related adverse events at each dose level in the two groups, treatment vs. placebo) will be mostly descriptive and proportions and confidence intervals will be calculated. Contrasts involving repeated measures on the same participants can be tested with McNemar's test (for two correlated proportions) or GEE models/GLMMs. Contrasts for independent data can be tested with standard two sample proportions test and with GLMs. Proportions, logistic regression, and relative risk regression can be applied to binary outcomes over a fixed period of time, and Poisson models can be applied to counts or events over time.
- 2. Vital signs, orthostatic blood pressures, physical exam, EKG, and labs (hematology, complete metabolic profile, urinalysis) will be done during study visits. For vital signs and labs, data will be analyzed as a simple two-period trial. Means and confidence intervals will be presented pre and post treatment by treatment group, and for the change scores by treatment group. A two independent sample T-test will compare the means of the change scores between the treatment groups. More complex situations can be analyzed with longitudinal regression models.
- 3. Standardized assessment tools (MoCA, Cognition assessment battery, Anxiety short form, NPI, SCOPA-Sleep, ISI, DBAS-16, Pittsburgh Sleep Quality Index, RBDSQ, QUIP-RS, C-SSRS, Depression short form, Emotional Behavioral dyscontrol short form, Fatigue severity scale, MDS UPDRS, UDysRS, Pain Intensity 3a short form and Pain Intensity 4a short form, IRLS, PDQ-39 and EQ-5D-5L) and lab tests, the data will be analyzed as a simple two-period trial. Means and confidence intervals will be presented pre and post treatment by treatment group and for the change scores by treatment. A two independent sample T-test will compare the means of the change scores between the treatment groups. More complex situations can be analyzed with longitudinal regression models.
- 4. Proportion of participants who drop out of the study due to study drug intolerance. Analysis (proportions of participants who drop out of the study due to study drug intolerance in the two treatment groups) will be mostly descriptive, and proportions and confidence intervals will be calculated. Proportion differences between groups can be compared with the standard test.

**Exploratory Outcome Measures:** The efficacy of CBD on cognition, psychosis, sleep, daytime sleepiness, mood, fatigue, pain, impulsivity, other motor and non-motor PD signs, restless legs syndrome, REM sleep behavior disorder, quality of life, and plasma levels of cytokine are evaluated using the aforementioned assessment tools. The change from baseline to end of 2.5 mg/kg/day is compared.

Exploratory analyses: To study the efficacy of CBD on cognition, anxiety, psychosis, sleep, daytime sleepiness, mood, fatigue, pain, impulsivity, other motor and non-motor PD signs, restless legs syndrome, REM sleep behavior disorder, plasma levels of cytokine, and seborrheic dermatitis.

Exploratory outcomes include assessments of cognition, anxiety, psychosis, sleep, daytime sleepiness, mood, fatigue, pain, impulsivity, other motor and non-motor PD signs, restless legs syndrome, REM sleep behavior disorder, and plasma levels of cytokine. Continuous outcomes will be analyzed in the same way as tremor. Transforms or non-parametric methods will be applied as necessary. Non-continuous outcomes will be analyzed with generalized estimating equations models, generalized mixed models, and McNemar's test for binary outcomes.

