#### THC vs. CBD

Many clinicians who suspect cannabis may have a positive effect upon a particular patient group do not know the cannabinoid profile that is being used. Without knowing the composition, it is impossible to draw any conclusions simply because of the huge variety of strains utilized. CBD is present to a lesser extent in street marijuana, and has been shown to limit THC's so called "psychoactive" effect [Bhattacharryya S et al, 2010; Hayakawa K, et al. 2008; Atakan Z. 2012], meaning the "high."

CBD acts in some experimental models as an anti-inflammatory, anticonvulsant, anti-oxidant, antiemetic, anxiolytic, and antipsychotic agent, and therefore has potential beneficial medical uses [Zhornitsky S, et al. 2012; Crippa JA, et al. 2011; Iuvone T, et al. 2009; Vuolo F, et al. 2015]. Further, animal studies suggest that CBD is neuroprotective, perhaps due to reported anti-oxidative [Lastres-Becker I, et al. 2005; García-Arencibia M et al. 2007; Hayakawa K, et al. 2007] and antiinflammatory actions [Mecha M, et al. 2013]. The ratio of THC to CBD plays a role in the preparation's therapeutic outcome: strains of cannabis with higher concentrations of CBD did not produce short-term memory impairment vs. strains with similar concentrations of THC, but lower concentrations of CBD [Englund A et al. 2013]. THC is associated with psychosis, cognitive impairment, anxiety, and psychomotor slowing [Hall W., et al. 1998, Hindocha C., et al. 2017]. **Thus, CBD has likely beneficial effects in PD, but THC may have harmful effects.**  CBD undergoes a significant first-pass effect leading to the formation of a number of metabolites, most notably, 7-hydroxy-CBD and CBD-7-oic acid [Agurell, S. et al. 1986; Harvey, D.J. 1990]. The half-life of CBD in humans was found to be between 2–5 days following oral administration. Bioavailability of oral CBD in humans was found to be around 6%, [Agurell, S. et al. 1986; Consroe, P. et al. 1991; Ohlsson, A. et al. 1986; Guy, GW. et al. 2004]. Oral administration of CBD (~700 mg) over six weeks to 14 Huntington's disease patients resulted in a low, narrow plasma range of 5.9–11.2 ng/mL [Consroe, P. et al. 1991].

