#### **Secondary Outcome Measures:**

**1**. To evaluate the safety and tolerability of CBD in PD:

1.1 By examining the frequency of study-related adverse events at each dose level between the two groups (treatment vs. placebo). Adverse events are measured at study visits, starting with an open ended question (Do you notice any effects, good or bad, of the study drug?) and followed by a series of yes/no questions regarding adverse effects (including previously reported adverse effects of CBD and general common adverse effects of medications and the hepatotoxicity), and all the effects we hypothesize in the study. For each adverse and beneficial reported effect, further questions will be asked, such as when did the effect start and how is it progressing, etc. In addition, since a major dose limiting effect is somnolence, the daytime sleepiness part of the SCOPA-sleep is included.

Tolerability is judged and supervised by PI and sub-I (who are MDs), based on their clinical expertise.

Abuse-related AEs will also be collected at screening, each dose assessment visit, liver function monitoring visit, and safety follow up visit. The abuse-related AEs is provided by MedDRA Preferred Terms (PTs), including:

Euphoria-related terms: Euphoric mood, elevated mood, feeling abnormal, feeling drunk, feeling of relaxation, dizziness, thinking abnormal, hallucination, inappropriate affect. Terms indicative of impaired attention, cognition, and mood: Somnolence, mood disorders, and disturbances.

Dissociative/psychotic terms: Psychosis, aggression, confusion, and disorientation. Related terms not captured elsewhere: Drug tolerance, habituation, drug withdrawal syndrome, substance-related disorders.

The Abuse-related AEs will be collected and recorded on a CRF that includes timing of the event, duration, severity, indication if more than one event was observed simultaneously, if other drugs were taken by subjects at the time of the event, correlation between the onset of the event, and the use of study drug.

Well trained investigators will capture and report cases of abuse, misuse, or addiction and monitor for drug accountability discrepancies before starting trials.

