The study is a randomized, placebo controlled, double-blind parallel design with two treatment arms, each of approximately 2-3 weeks duration. In the 2-3 week treatment phase participants will start study drug and titrate up to the maximum tolerated or targeted dose (2.5 mg/kg/day of CBD). Each participant will have a screening visit, baseline visit within four weeks, 2 dose assessment visits (1.25 mg/kg/day and 2.5 mg/kg/day), and a safety visit (5 visits total). Participants will be evaluated at each dose level for monitoring adverse events, as well as changes in medical history and concomitant medications. Further, in case CBD alters the reliability of self - report, repeated measures will be taken on the third to fifth day at each dose during the clinic visits or at home. The assessments include the assessment of tolerability and symptoms of hepatotoxicity, SCOPA-sleep, Anxiety short form, Depression short form, Emotional and behavioral dyscontrol short form, and EQ-5D-5L. Participants are called 3 and 7 days after stopping the study drug to check for signs of withdrawal. At dose assessment visits, urinary CBD and metabolites will be tested. To maximize compliance the coordinator calls the participant to remind them the next day's clinical visit. To increase compliance with taking study drug, participants will be asked to fill out a diary at home. The diary will be a record of the date and time participants take study drug, dose of the study drug, and adverse and beneficial events. Study drug is dispensed at the baseline visit. Participants will measure their tremor using Tremor GUI MATLAB twice a day (two hours after breakfast dose and two hours after dinner dose) for two consecutive days after screening visit, three consecutive days prior to baseline and each dose assessment visit, as well as during the clinic visits. To evaluate the possible somnolence effect of CBD, participants will be evaluated their alertness before and three hours after they take the study drug at baseline visit.

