- 4. Adverse events and serious adverse events will be reported from the time of study drug administration until the last study visit or death, whichever occurs first, according to mandated guidelines.
- 5. All adverse events and serious adverse events will be followed until resolution (or return to baseline status), or until the condition stabilizes or is otherwise explained, or until participant dies or is lost to follow-up.
- 6. Safety assessments are comprehensive and include vital signs, history and physical examination, concomitant medications collection, EKGs, safety labs (Hematology, Hemoglobin A1C, Complete Metabolic Profile and Liver Function Tests), blood and urinary cannabis and metabolites analysis, MoCA, QUIP-RS, C-SSRS, NPI, SCOPA-sleep, Anxiety short form, Depression short form, Emotional and behavioral dyscontrol short form, Fatigue Severity Scale, Pain Intensity and Interference short form, study drug compliance check, adverse event check, and urine and blood pregnancy testing.

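### Section F closes the analysis window with the 2.5 mg/kg/day dose and compares adverse events by dose level, so no CBD-versus-placebo comparison is specified for the off-drug period (nominally Days 15–28)

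*Combined protocol and SAP*

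**What the plan says.** Section F sets one window for all three tiers of outcome: "The primary, secondary and exploratory outcomes will be analyzed as below from baseline to the end of 2.5 mg/kg/day". It then describes the secondary aim, which "is to examine safety and tolerability of CBD and the effect of CBD on severity and duration of intractable tremor and other symptoms in PD". That places safety inside the tier that the window governs.

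The adverse-event comparison is organised by dose. Secondary outcome 1.1 in Section IV.A defines it thus: "By examining the frequency of study-related adverse events at each dose level between the two groups". The first safety item of Section F repeats it: "frequency of study-related adverse events at each dose level in the two groups, treatment vs. placebo". Section C.1 names two dose assessment visits, 1.25 and 2.5 mg/kg/day, and lists the safety visit separately.

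Collection runs longer. Section D, item 4: "Adverse events and serious adverse events will be reported from the time of study drug administration until the last study visit or death". Section C.1: "Participants are called 3 and 7 days after stopping the study drug to check for signs of withdrawal". Visit 5, about two weeks after the last dose, includes an adverse-event check, an investigator evaluation for withdrawal, and most of the rating scales. Outcome 1.1 also has abuse-related events collected at that visit, and its list of terms includes drug withdrawal syndrome.

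**The concern.** Withdrawal effects can appear only once dosing has stopped, so a comparison that ends with dosing cannot show them. Many complaints that might arise in this period, such as poor sleep, anxiety and fatigue, are common in Parkinson's disease and hard to interpret without the placebo arm beside them.

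The second hypothesis in Section I is that CBD is safe and tolerated. If the analysis follows Section F literally, that conclusion would rest on the on-drug period, and the randomized comparison of what happens after stopping would go unused although the data are collected. If Section F is instead read loosely, the safety period is left to be settled later, possibly after unblinding.

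**Working it through.** The plan gives no figure on this point, and its sample-size calculation does not bear on it. The check compares what is collected with what is compared, then sizes the gap.

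**1. Where each record falls under the written rule**

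| Collected | Source | Planned comparison by arm |
|---|---|---|
| Adverse events at 1.25 and 2.5 mg/kg/day | Outcome 1.1; Section F, safety item 1 | Yes, by dose level |
| Rating scales up to Visit 4 | Outcome 1.4; Section F, safety item 3 | Yes, as change scores |
| Adverse events with onset after the last dose | Section D, item 4 | None stated |
| Withdrawal calls, 3 and 7 days after stopping | Section C.1 | None stated |
| Withdrawal evaluation and scales at Visit 5 | Procedures at each visit | None stated |

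Two other passages do not fill the gap. Secondary outcome 10 adds a comparison at the end of 1.25 mg/kg/day, which lies inside the window. The by-arm tabulation of withdrawals in Section C.5 concerns people leaving the study, not symptoms of drug withdrawal.

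For example, somnolence starting on Day 8 is counted at 2.5 mg/kg/day. Insomnia starting on Day 16 belongs to neither dose level.

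**2. Length of the off-drug period**

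Inputs from Section C.2 and Appendix 1: Visit 4 on Day 14 (+4), so Days 14–18; Visit 5 on Day 28 (±4), so Days 24–32. Off-drug days = Visit 5 day − Visit 4 day; share = off-drug days ÷ Visit 5 day.

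| Case | Visit 4 | Visit 5 | Off-drug days | Share |
|---|---|---|---|---|
| Nominal | 14 | 28 | 14 | 14/28 = 50% |
| Shortest | 18 | 24 | 6 | 6/24 = 25% |
| Longest | 14 | 32 | 18 | 18/32 = 56% |

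The two extremes let the visit windows vary independently. If Visit 5 is held at two weeks after stopping, as Section C.2 describes it, the period stays at 14 days.

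**3. Drug remaining after the last dose**

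Input from Section II: "The half-life of CBD in humans was found to be between 2–5 days following oral administration". Assumption: simple exponential decay from the end-of-dosing level, so fraction remaining = 0.5^(t / half-life).

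| Days after stopping (t) | Half-life 2 days | Half-life 5 days |
|---|---|---|
| 3 (first call) | 0.5^1.5 = 0.354 | 0.5^0.6 = 0.660 |
| 7 (second call) | 0.5^3.5 = 0.088 | 0.5^1.4 = 0.379 |
| 14 (nominal Visit 5) | 0.5^7 = 0.008 | 0.5^2.8 = 0.144 |

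So the first week off drug, at least its early part, is still a period of appreciable exposure in the CBD arm. The second week is so only toward the longer half-life.

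**The case against.** The best defence is that the text is incomplete rather than exclusionary.

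- Safety item 1 refers to events gathered at study visits, and Visit 5 is one of the five.
- Outcome 1.1 itself reaches Visit 5 through the abuse-related events.
- Section F permits Poisson models for events over time and longitudinal models for more complex situations.
- Appendix 1 shows a dosage of 0 after Day 14, which could be tabulated as a level of its own.
- The window sentence suits change scores better than event counts, and the safety list announces five approaches but shows four, so its silence is weak evidence of intent.

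These points establish ambiguity, and that part stands. They do not supply a comparison. The models are optional and name no off-drug period, the text never calls 0 a dose level, and all of them sit under a window sentence that covers every tier.

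It is also fair to say that drug withdrawal is not a stated hypothesis, that Section D presents post-stopping follow-up as participant protection, and that the adverse-event analysis is described as mostly descriptive. This limits the importance of the point without removing it.

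A reader might infer that late events are lost, or that no analysis could ever use them. The documents do not support that. Adverse events are recorded to the last visit and followed to resolution or stabilization, related serious events after treatment are documented and reported, and abnormal end-of-treatment liver tests are repeated at follow-up. Nor is every symptom first mentioned after Day 14 left out: one reported on Day 17 that began on Day 13 belongs to 2.5 mg/kg/day by onset.

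**Conclusion.** The concern holds as a gap in the prespecified safety comparison. As written, the window and the dose-level rule leave events with onset after the last dose, and the withdrawal findings, outside any stated CBD-versus-placebo comparison. The period is 14 of 28 days on the nominal schedule and 6 to 18 days across the visit windows.

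The residual-drug figures rest on the protocol's half-life range and an assumed exponential decay. They show why the period is relevant to drug effects. They do not predict a difference between arms. A reader might also take the 50% to mean that half of the drug's adverse events would be missed. It is a share of calendar days, not of events, and nothing in the documents gives event rates for this period. Likewise, a claim that participants remain substantially exposed throughout follow-up fails at a 2-day half-life, where less than 10% remains from day 7 onward.

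The point should be addressed because it bears on the safety part of the secondary aim. It does not touch the primary analysis or the sample size.

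**What to change.** In Section F:

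1. Limit the window that closes with 2.5 mg/kg/day to the efficacy change scores.
2. For outcome 1.1 and safety item 1, keep the dose-level tables and add a comparison by arm of adverse events with onset from first dose to the last visit.
3. Tabulate separately by arm the events with onset after the participant's last dose, together with the findings of the two withdrawal calls and the Visit 5 withdrawal evaluation. Assign events by onset date, not report date.
4. If Visit 5 scales are summarised by arm, label this as descriptive only. Section F plans no multiplicity adjustment across outcomes, and there are about 30 participants per arm.

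The cost is a few sentences and a few extra tables, settled before unblinding. The reported event rate may look somewhat less favourable. No additional data, visits or participants are needed.

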## Results

Figure 1 shows the trial profile. Data from all participants that took the study drug were analyzed for safety and tolerability, while only data from those that completed a final dose assessment were analyzed for efficacy. Table 1 shows the baseline clinical and demographic characteristics of safety and efficacy analysis groups.

Figure 1. Open label study profile

[figure not shown]

Table 1. Baseline demographics of the safety and efficacy analysis gro
--

	Safety analysis group (n=13)	Efficacy analysis group (n=10)
Age (years) (mean, SD)	68.1 (6.05)	68.7 (6.65)
Male (n, %)	10 (77%)	8 (80%)

Total MDS UPDRS score (mean, SD)	39.23 (13.32)	43.20 (12.21)
Motor MDS UPDRS score (mean, SD)	22.92 (9.30)	24.70 (8.93)
Disease duration, years (mean, SD)	6.08 (3.99)	6.30 (4.52)
Hoehn & Yahr Scale (mean, SD)	1.73 (0.56)	1.75 (0.59)
MoCA (mean, SD)	28.1 (1.63)	27.9 (1.60)
Levodopa Daily Dose Equivocation (LDDE) (mean, SD)	398.3 (331.00)	443.8 (348.97)

The demographics show that, in general, the participants had an age of onset consistent with the general population of persons with PD and they had early to early-middle stage PD. Generally they had mild bilateral motor symptoms, walked without assistance, had disease for six years, and required a relatively low dose of medication for their motor symptoms. An entry criteria required them to have a relatively significant tremor, but it would be a resting tremor and thus as a general group these participants likely had very little disability. These participants had scored in the normal range on the entry cognitive screening test.

The original protocol was that participants start at 5 mg/kg/day and titrate up to 25 mg/kg/day. Participants were to remain on each dose for three days, until the maximal tolerated dose was reached, and they were to be on that dose for 10-15 days, during which time they came in for an assessment visit.

Due to AEs experienced by our first five enrolled participants and the recommendations of the two PharmDs in our study, the protocol was changed to a slower titration and the maximal targeted dose was reduced from 25 to 20 mg/kg/day, since December 2016. There had been increased AEs and no evidence of additional benefit in the five participants beyond 20 mg/kg/day. Therefore, participants started at 5 mg/kg/day and increased every three to five days by 2.5 to 5 mg/kg/day until reaching a maximal targeted dose (20 mg/kg/day) or experiencing intolerable adverse effects.

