#### Discussion

The primary outcome was safety and tolerability. Generally, the study drug, Epidiolex®, was well tolerated. While adverse effects, mainly somnolence, fatigue, and diarrhea, were frequent, they were generally mild, and there was a relatively low percent of participants, i.e., 23%, that stopped study drug due to intolerability, and no clinically significant abnormalities in testing except for elevated liver enzymes.

Regarding the elevated liver enzymes, GW had seen elevations in their pediatric group, but the pattern was hepatocellular, not cholestatic as in our population. Perhaps age contributed to the difference, since GW had not used Epidiolex® in persons over age 50. In our study liver enzymes were only checked on the highest dose and most of the affected participants were asymptomatic, so it is not clear at what dose the liver enzymes became elevated. [name], Hepatologist, reviewed detailed information on these participants and of all the liver function results in all participants, commented that the changes may represent early liver injury and felt that with close monitoring it was reasonable to move on with the next study. She will be a consultant on the randomized controlled parallel study. The DSMB also reviewed all the data and noted that all changes resolved with cessation of treatment and discussed the possibility the elevations may be related to medication vehicle, i.e., sesame oil. Most participants were talking 10-20 ml per day on the final maximal dose when the testing occurred. The DSMB agreed with continuation of the study with the monitoring plan in this protocol.

Solid conclusions regarding efficacy are not possible from an open label trial, but this study suggested benefit in motor symptoms, night-time sleep, and emotional dyscontrol.

In summary, findings from the open label study suggest that CBD may be efficacious in PD, and that a lower dose may offer the best benefit to risk ratio, compared to the higher dose that GW reports is useful in pediatric epilepsy. Therefore, a lower dose will be used in the randomized controlled parallel study.

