## **IV. Research Methods**

#### A. Outcome Measure(s):

**Primary Specific Aim:** To evaluate the efficacy of CBD on motor symptoms in PD. **Primary Outcome Measures:** Change of MDS-UPDRS Part III (motor examination) from baseline to the end of 2.5 mg/kg/day of CBD. MDS-UPDRS Part III assesses the motor signs of PD. **Secondary Specific Aim:** To examine safety and tolerability of CBD and the effect of CBD on severity and duration of tremor, night-time sleep, rigidity, emotional dyscontrol, anxiety, and pain in PD.

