#### Sample Size Justification

Using preliminary data we estimate a standard deviation for the within treatment UPDRS Motor change scores, post treatment compared to baseline, of 6.72, and a correlation between the paired observations of the change score of 0.75. Consistent with the preliminary data we anticipate a mean baseline UPDRS Motor score of 23, so a 25% treatment effect would have a magnitude of 5.75, less than the within treatment mean change score of magnitude 6.10 observed in the preliminary data. The estimated standardized effect size is 0.856. Therefore, the two independent samples T-test, testing for a between treatment difference on the within treatment UPDRS Motor change scores, at alpha = 0.05, would require a total sample size of 46 patients for 80% power, and 60 patients for 90% power. Compensating for the possibility of 20% drop out, we would need to recruit 58 patients for 80% power, and 75 patients for 90% power. Thus we plan to recruit 75 patients with a goal of having at least 60 patients complete the study.

Since other outcomes are either descriptive and/or exploratory, and sample size is limited, adjustment for multiple testing adjustments are not planned across different outcome variables.

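### The primary t-test uses only patients with a final Part III score and omits baseline, Visit 3 and the age stratum; separately, the age strata leave out ages 81-85

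*Combined protocol and SAP*

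**What the plan says.** The primary outcome (A. Outcome Measure(s)) is "Change of MDS-UPDRS Part III (motor examination) from baseline to the end of 2.5 mg/kg/day of CBD". Section F, Data Analysis Plan, states "Intention to treat concept is followed" and then names the primary test: "A two independent sample T-test will compare the means of the change scores between the treatment groups". Modelling comes second: "Longitudinal regression models will be fit for further analysis, including adjusting for covariates if necessary". No covariates are named. The section also says "The analysis will be performed in accordance with the analysis plan devised prior to unblinding".

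The Sample Size Justification takes 60 completers to 75 recruits, "Compensating for the possibility of 20% drop out". Neither it nor Section F defines an analysis set, an imputation rule or a missing-data assumption for the primary outcome.

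Other sections bear on the point:

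- **Procedures at each visit:** the full MDS-UPDRS is done at Visit 3 (the lower dose) as well as at Visit 4.
- **C.5, Participant stopping rules:** an early-termination visit with efficacy assessments is to be attempted. The text does not say that these include Part III or how such a score is used. Appendices 1 and 6 list no such visit.
- **C.3:** randomisation is stratified by age (40-60, 61-80) and by Hoehn and Yahr stage (1-2.5, 3-5).
- **Inclusion criteria:** ages 40 to 85, and an ON motor score above 20.
- **Section III, Results:** in the pilot, "only data from those that completed a final dose assessment were analyzed for efficacy", which was 10 of 13 patients.

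**The concern.** A change score needs a final score. A randomised patient without one cannot enter the primary test, yet the plan commits to intention to treat and budgets for up to one patient in five dropping out. Different readings of that commitment give different primary estimates from the same data.

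The completer t-test is unbiased if dropout is unrelated to motor change, or if both its rate and its reasons are the same in the two arms. Neither condition can be confirmed in advance.

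The test also sets aside three items already collected that could sharpen the estimate or reduce its dependence on completers: baseline Part III, Visit 3 Part III and the age stratum. The age strata themselves do not cover the eligible age range.

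**Working it through.** **1. The plan's own figures.** Effect 5.75, SD 6.72, two-sided alpha 0.05 (Sample Size Justification; two-sided is assumed because it reproduces the figures). The standardised effect is 5.75/6.72 = 0.856. The noncentral t gives a total of 46 for 80% power and 60 for 90%; 46/0.8 = 58 and 60/0.8 = 75. All the stated figures reproduce. Power with 30 per arm is 90.3%.

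**2. The missing-score rule matters even with random dropout.** Assume 20% missing at random in each arm of 37.5.

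- Completers only: expected difference 5.75, power 90.3%.
- Baseline carried forward: 0.8 x 5.75 = 4.60. The variance per arm is 0.8 x 6.72² + 0.16 x (mean change)². Power is 88.4% if the placebo mean change is 0 and 86.4% if it is -2.

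Both could be described as following intention to treat.

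**3. Equal dropout rates are not enough.** Assume no drug effect and 20% dropout in each arm. On CBD it is random. On placebo it is the 20% with the worst Visit 3 change. Let r be the correlation between Visit 3 and Visit 4 change (assumed 0.43-0.6). The placebo completers' mean shifts by r x 6.72 x φ(0.842)/0.8 = r x 6.72 x 0.35, which is 1.0-1.4 points. Softer tracking, by simulation, gives about 0.5-1.1. Here the bias runs against CBD; with the arms reversed it would favour CBD.

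**4. Baseline adjustment.** Pilot Part III SDs (n=10) are 8.93 at baseline, 9.66 at the end and 6.64 for change.

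- Correlation: (8.93² + 9.66² - 6.64²)/(2 x 8.93 x 9.66) = 0.748.
- Slope: 0.748 x 9.66/8.93 = 0.81, SE 0.254, 95% CI 0.22 to 1.39.
- Residual variance relative to change-score variance: 0.875 with equal SDs and correlation 0.75, (1 + 0.75)/2; 0.934 with the pilot SDs; 0.967 with the pilot baseline truncated at the entry score of 20; 1 if the slope is 1.

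Power with 60 completers comes from the noncentral t with k covariates, 58 - k degrees of freedom and variance multiplied by 1 + k/(57 - k):

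| Variance ratio | Baseline only (k=1) | Baseline and age, age explaining nothing (k=2) |
|---|---|---|
| 0.875 | 93.2% | 92.8% |
| 0.934 | 91.6% | 91.1% |
| 0.967 | 90.7% | 90.2% |
| 1 | 89.8% | 89.2% |

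In simulation, a model that also uses Visit 3 (75 randomised, 20% missing at random, slope 0.75-1, assumed residual visit correlation 0.43-0.6) changed power by -0.3 to +4.6 points relative to the t-test.

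**5. Strata.** Pilot ages are 68.1 (SD 6.05) or 68.7 (SD 6.65). A normal distribution puts 0.015 to 0.028 of patients between 81 and the end of age 85. Times 75, that is 1.1 to 2.1 patients, with a 68-88% chance of at least one. Pilot Hoehn and Yahr of 1.73 (SD 0.56) or 1.75 (SD 0.59), cut at 2.75 to 3.0, puts 0.9 to 3.4 of 75 in stage 3-5.

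**6. Tipping point.** Shift the missing CBD Visit 4 scores by δ towards worsening, with 20% missing. Significance is lost where 5.75 - 0.2δ = 2.002 x √(6.72² x 2/30 + 0.16δ²/37.5). This gives δ of about 10. With an observed effect of 4.5, δ is about 5.

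**The case against.** **The t-test is valid, and the plan is to be fixed before unblinding.** Both are true. An open choice would be made blinded. However, no fuller plan is in the documents, and writing the rule now only carries out that intention.

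**Dropout is not the same as a missing score.** This stands. The 20% is an allowance, and early-termination assessments may supply some scores. The calculations that treat every dropout as missing are therefore on the high side. Visit 3 is not wasted either: secondary outcome item 10 compares it between arms. It just cannot inform the primary test.

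**A reader might infer that the primary result will be biased, probably towards CBD.** The documents do not support that. The pilot reports that "there was a relatively low percent of participants, i.e., 23%, that stopped study drug due to intolerability", but it was open label and the protocol puts its doses at more than seven times those used here. Its three non-completers back-calculate to a mean baseline of (13 x 22.92 - 10 x 24.70)/3 = 17.0. That rests on three people, below this trial's entry score, and the difference from completers has a confidence interval spanning zero (-5.4 to 20.8).

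**The model is not a cure.** This also stands. It assumes missing at random. In an assumed scenario where dropout follows the unseen final score, simulated bias was 2.0 points for the t-test and 1.4-1.8 for the model. That is why a sensitivity analysis belongs with it.

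**Adjustment is a preference.** In part. The gain is small and turns into a small loss if the slope is 1, which the pilot interval allows. Ignoring prognostic strata makes the t-test conservative rather than invalid.

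**Conclusion.** The point holds as an improvement to the primary analysis and as one plain contradiction. The t-test covers only patients with a final score, no rule says what happens to the others, and baseline, Visit 3 and the age stratum are left out. At the planned effect with 20% missing at random, the choice between completers and baseline carried forward alone moves the expected estimate from 5.75 to 4.60. Baseline adjustment takes power from 90.3% to 90.7-93.2%, or to about 89.8% if the slope is 1. The variance ratios rest on ten pilot patients and on the plan's correlation of 0.75, read here as baseline with final score.

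Three stronger readings should be resisted. The sample size is not wrong, since every stated figure reproduces. Equal dropout rates would neither establish nor rule out bias, because the reasons matter too; the bias figures are assumed scenarios. Nor does stratified randomisation mean that Hoehn and Yahr must enter the model, because its upper stratum may hold only about 1-3 of 75 patients.

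The gap at ages 81-85 needs no assumption. Only its expected size, 1-2 patients, depends on the pilot age distribution.

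**What to change.** 1. Make the longitudinal model primary, in all randomised patients as randomised. Treat Part III at baseline, Visit 3 and Visit 4 as outcomes, with a common baseline mean across arms, arm-by-visit effects after baseline, and the age stratum. Test the arm contrast at Visit 4. Having baseline as an outcome keeps in patients with only a baseline score, whom a model with baseline as a covariate would drop. Do not require the Hoehn and Yahr stratum. Keep the t-test as supportive.
2. State that early-termination efficacy assessments include Part III. A score on or before day 4 fills Visit 3 only if Visit 3 is empty. A later score fills Visit 4 only if Visit 4 is empty. No early-termination score replaces an observed one. Repeat the analysis with these scores set to missing.
3. Add a delta-adjusted analysis that worsens missing CBD Visit 4 scores in steps until significance is lost, and report the tipping point.
4. Reconcile the age strata in C.3 with the inclusion criteria so that every eligible age has a stratum.

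The cost is analysis-plan wording, one stratum label, a few degrees of freedom, reliance on missing at random and a little more analysis work. It needs no new visits, data or patients.
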